
tumours discovered through screening (1;2). In a patient monitoring study pilot in the Dutch screening organisation "Zuid-West", data on the staging differences between screening tumours and interval cancers have been collected. Interval cancers are more frequently stage III (12%) or IV (15%) compared to screen-detected tumours (4% and 6% respectively) (1). A Finish study shows that the 5-year survival probability is 95% for women with screen-detected tumours and 78% for interval cancers (2). Women with very dense breasts have a higher risk of developing screen-detected tumours and even more so of developing interval cancer (4;5;7;8). Five per cent of all women who participate in the population-based screening program have very dense breasts (>75%) and 13% of the interval cancers is found in this group (6).
Women with very dense breasts most likely have a higher chance at developing interval cancers because the large amount of fibroglandular and stromal tissue in the breast could mask the potential presence of a tumour during mammographic screening. There are no indications this would be caused by tumours growing faster in this group of women (4;16).
4. Treatment options and prognosis
The most commonly used treatments for breast cancer are: surgery, radiotherapy, chemotherapy, hormonal therapy and treatment through monoclonal antibodies. Most women with breast cancer receive a combination of the above-mentioned treatment methods. The choice and the sequence of the different treatments depends, among others, on the characteristics of the tumour, the stage of the disease, age and menopausal status.
The breast cancer prognosis after treatment depends on the stage at diagnosis (see graph below). The 10-year survival probability varies from very good (>90%) at stage I to very bad at stage IV (<10%) (see graph). Treatment is not different for different density categories since there are no indicators of differences in prognosis of tumours in the same stage. The prognosis of interval cancers, which also occur more frequently among women with very dense breasts, is worse than that of tumours discovered through regular screening, because the stage at diagnosis is less favourable (1;2) (see Section 3. Natural course of the disease).

5/ 6. not applicable

7. Population-based screening program alternatives

Primary prevention

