
The drawback of the above-mentioned studies is the cross-sectional character, i.e. that all women in the studies have been offered all imaging techniques described in the study. Because of this set up, it is not clear whether MRI reduces the number of interval cancers, whether there is a difference in staging of the tumours found, and whether it does lead to a less aggressive treatment.

In a randomised design like we propose in this experimental populationbased screening study, we actually aim to get a better understanding of these clinically important outcome measures and the number of false positives (and unnecessary biopsies). The randomised design, the outcome measures chosen and the size of this experimental population-based screening study will generate the necessary weight of evidence on the efficacy of adding MRI to the current breast cancer screening programme among women with very dense breasts.

2. Other important implications

Investigating the value of adding MRI to the current breast cancer screening programme among women with very dense breasts is also important for younger women (45-49 years old). These women currently fall outside the Dutch population-based mammography screening program because it is not cost-effective. The screening is not cost-effective partly because, among other reasons, many women in this age group have very dense breasts so the sensitivity of mammography screening is limited. If this experimental population-based screening study reveals that MRI examinations are effective in detecting breast cancer at an early stage among women with very dense breasts, then this will also be important information for a potential cost-effective strategy for women of the age of 45 to 49. Another important effect is obtaining more insight into the relationship between density and breast cancer risk.

Part 5. Description of the population-based screening study (max. 300 lines)

1. Design, sites
Described in Part 7.
2. Information, communication, complaints, report
Described in Part 7.
3. Objectives, feasibility, actual results
Objective of this experimental population-based screening study is to detect breast cancer in an early and better treatable stage among women with

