There are no studies known on the use of MRI for breast cancer screening in this target population. As has been described extensively in Part 3. Screening strategy , MRI is in terms of sensitivity the most promising screening technique. However, MRI studies have so far been limited to women with a BRCA1 or BRCA2 mutation or women with a very strong family history of breast cancer. This strategy turned out to be cost-effective and the American Cancer Society and American College of Radiologists (www.acr.org) now recommends that women, who have a 20-25% lifetime risk of developing breast cancer throughout their lives, should get an MRI

each year (in addition to mammography) starting from the age of 30 (31).
6. Research design
Design The study includes a randomised controlled trial (RCT) with rates of (extra) detected tumours, interval cancers and tumour stage distribution as the primary outcome measures. Many studies that evaluate the new screening methods use a so-called cross-sectional paired design whereby the participants receive both the 'old' as well as the 'new' test. This indicates how many more tumours are discovered by the new test compared to the old test, but it does not indicate in which stage the tumour with each of the tests could be detected. A similar major problem is that the proportion of interval cancers cannot be compared between the two tests. This is because all tumours detected by one of the two tests will be treated; only the tumours that are missed by both tests could appear as interval cancers. A decline in the number of interval cancers compared to the old method is important to show if the new screening test really is effective and does not cause merely more overdiagnosis (in other words, the detection of tumours that would never have become symptomatic during a woman's lifetime). For this reason, an RCT with parallel groups is necessary.

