Indicators of screening effectiveness The extra number of tumours detected by MRI, but missed by mammography, shall be described as well as the recall rate, the positive predictive value (and the false positive percentages) of the MRI and the number of biopsies per positive MRI test, with the corresponding 95% confidence intervals.
The primary outcome is the comparison of the interval cancer proportions between the study groups (Chi-square or Fisher's exact test in case of small numbers). Tumour size, stage and degree of the tumours will be compared between the arms as well as the distribution of histological and molecular subtypes. With respect to tumour size, the difference between means will be tested using the Student's T-test. If not normally distributed, the medians will be calculated and the differences will be tested using the Mann-Whitney U test. Differences in stages, grade, histological and molecular subtypes are tested using Chi-square or Fisher's exact test in case of small numbers.
A problem already mentioned before, with the single consent version of the pre-randomisation design, is the dilution of the effect by non-participation in the intervention group after randomisation. Nevertheless, to be able to reach a true (nondiluted) estimation of the effect of the MRI, the analysis method of Cuzick et al. (35) will be used, which was specifically designed for these kinds of screening studies.
Estimation of mortality reduction Calculating the actual mortality reduction requires a very long follow-up period and an even larger study population than proposed here. Breast cancer screening simulation models are a less expensive and faster approach to study the mortality reduction rate of this intervention. We use the MISCAN simulation programme that was specifically designed to build cancer screening models and also to analyse and explain the cancer

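### Stage and grade are ordered, but the plan tests them with an unordered chi-square or Fisher test, a valid but inefficient choice for detecting a shift to earlier stage

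*Combined protocol and SAP*

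**What the plan says.** Part 7, section 9 (Indicators of screening effectiveness) handles four tumour characteristics in one sentence: "Differences in stages, grade, histological and molecular subtypes are tested using Chi-square", or Fisher's exact test when numbers are small. Two of them, stage and grade, are ordered. The other two, histological and molecular subtype, are not. No trend test, rank test or ordinal model is named for stage or grade anywhere in the document, and their categories are not defined. For tumour size, the same paragraph does provide a rank test when the data are not normal: "the medians will be calculated and the differences will be tested using the Mann-Whitney U test".

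On the role of stage, the Design text in Part 7, section 6 lists "rates of (extra) detected tumours, interval cancers and tumour stage distribution as the primary outcome measures". Section 9 is narrower: "The primary outcome is the comparison of the interval cancer proportions between the study groups". Part 5, section 3 gives the objective as "to detect breast cancer in an early and better treatable stage among women with" very dense breasts. Part 4, section 1 counts a difference in staging among the questions that cross-sectional studies left open. No power is stated for stage or grade.

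**The concern.** The hypothesis has a direction along the stage scale: MRI should move tumours towards earlier stage. A chi-square test over four stages spreads its power over three degrees of freedom. It would give the same p-value if the stage labels were permuted, and Fisher's exact test on the full table ignores order too. Neither gives a direction or a single effect size.

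The comparison rests on few tumours, so lost efficiency matters. A real shift could be reported as a bare non-significant result and read as evidence that MRI does not change stage.

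**Working it through.** **1. The plan's own figure.** The only stated sample size is for interval cancers (Part 7, section 7). The mixed rate in the intervention arm is 0.66 × 1.44 + 0.34 × 4.4 = 2.446 per 1000. Against 4.4 per 1000, with 1:4 allocation, one-sided 5% and 80% power, the pooled-variance formula is

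n = [z₀.₉₅ √(1.25 p̄(1−p̄)) + z₀.₈₀ √(p₁(1−p₁) + p₂(1−p₂)/4)]² / (p₂−p₁)²,

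with p̄ = (p₁ + 4p₂)/5. This gives 7,243, against 7,237 in the plan. That calculation does not involve stage.

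**2. Expected tumours after one round and its interval.**
- Control, interval: 28,948 × 4.4/1000 = 127.
- Intervention, interval: 7,237 × 2.446/1000 = 17.7, about 18. The printed rate of 2.49 also gives 18.
- Intervention, MRI-detected: 4,776 × (4.40 − 1.44)/1000 = 14.1, about 14. This assumes that MRI finds only what would otherwise surface as interval cancer.

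The comparison is therefore about 32 versus 127 tumours.

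**3. Stage distribution.** Part 2, section 3 gives stage III and IV as 12% and 15% for interval cancers, and 4% and 6% for screen-detected cancers. That leaves 73% and 90% for stages I and II together. The I/II split is not given. It is assumed here: stage I at 30-40% of interval and 55-70% of screen-detected cancers.

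**4. Ideal ordered shift.** A one-degree-of-freedom test at two-sided 5% with 80% power has non-centrality (1.960 + 0.842)² = 7.85. The unordered chi-square at the same non-centrality has:

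| Categories | df | Power | Non-centrality for 80% | Extra tumours |
|---|---|---|---|---|
| 3 grades | 2 | 71% | 9.63 | 9.63/7.85 = 1.23, or 23% |
| 4 stages | 3 | 64% | 10.90 | 10.90/7.85 = 1.39, or 39% |

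**5. Simulation with the plan's counts.** Stages were drawn from multinomials, 18 + 14 versus 127 tumours, two-sided 5%, comparing Pearson chi-square (3 df) with a tie-corrected Wilcoxon test.

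| Stage I, interval / screen-detected | Chi-square | Wilcoxon |
|---|---|---|
| 40% / 55% (weakest) | 7% | 13% |
| 35% / 60% (central) | 12% | 21% |
| 30% / 70% (strongest) | 28% | 39% |

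Results are rounded and vary by about a point between runs. Wilcoxon is ahead in all nine splits tried. With no stage difference, both tests reject in about 5% of runs.

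**6. Sensitivity to which tumours count.** With all 8.0 cancers per 1000 counted (58 versus 232) and stage I at 25-36.5% of interval and 45-70% of screen-detected cancers, chi-square has 6-18% and Wilcoxon 7-28%.

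**7. Extra early tumours.** Let 32 intervention-arm tumours follow the interval-cancer stage mix exactly (stage I 35%) and add 10 stage I tumours. Wilcoxon then rejects in about 34% of runs and chi-square in about 24-25%, although no tumour has moved to an earlier stage.

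**The case against.** The strongest reply is that this is a preference about efficiency, not an error. The chi-square test is valid. The effectiveness question in Part 7, section 4, the sample size and the primary analysis in section 9 all concern interval cancers. This stands: the primary test and sample size need no change on this ground. Section 6 nevertheless gives stage a prominent role, so its test deserves to fit the hypothesis.

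Second, the change does not rescue the comparison. At 21% power in the central case, a real shift is still missed about four times in five. This also stands, and is a reason to report an effect estimate with its interval.

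Third, the loss depends on an assumed four-category table. If stage were analysed as I versus II-IV, a chi-square test in the central scenario would have about 21%, equal to Wilcoxon. In the four-stage table, the expected intervention-arm counts for stages III and IV are about 3.6 and 4.5, so Fisher's test might be used instead of the simulated Pearson test. Both remarks are fair. The plan defines no categories, however, and Fisher's test on the full table ignores order as well.

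Fourth, the ordered test has a cost. It reacts more readily to added early tumours (step 7), and the protocol itself raises overdiagnosis in Part 7, sections 6 and 11. This stands and shapes the fix.

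A reader might triple the one-round counts to claim adequate power over three rounds. The documents do not support that. Women are randomised after a negative mammogram only at entry. In the two later rounds mammography also detects cancers in both arms. At 0.45 × 8.0 = 3.6 per 1000, with no attrition, that is 2 × 7,237 × 3.6/1000 = 52 and 2 × 28,948 × 3.6/1000 = 208 further tumours, which dilute the contrast. Section 9 schedules the stage comparison after the first round and its two-year interval.

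**Conclusion.** The concern holds as a point of efficiency. Stage and grade are ordered, the expected effect follows the order, and the planned test ignores it. For an ideal ordered shift the loss is from 80% to about 64% (four stages) or 71% (three grades). With one-round counts, power is about 7-28% for chi-square and 13-39% for Wilcoxon. The one-round figures rest on four stage categories, the assumed I/II split, no excess tumours in the MRI arm and two-sided 5% testing; the plan states no sidedness for stage.

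Two stronger readings are not supported. One is that the trial's main conclusion is at risk: the interval-cancer comparison is separate and unaffected. The other is that an ordered test would make the stage comparison reliable: power stays below 40% over the range examined in step 5.

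**What to change.** In Part 7, section 9:

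- Prespecify the stage and grade categories, and say which tumours enter the comparison.
- Test both with a tie-corrected Wilcoxon-Mann-Whitney test (or a trend test), and report a proportional-odds common odds ratio with 95% CI alongside the full cross-table.
- Keep chi-square or Fisher's exact test for histological and molecular subtypes.
- Report the rate of advanced-stage cancer per woman randomised, by arm, with 95% CI. Extra early tumours do not enter its numerator, and it does not condition on having a tumour. Taking stage III-IV as advanced, the plan's inputs imply about 127 × 0.27 = 34 control cases and 18 × 0.27 + 14 × 0.10 = 6 intervention cases, so it will be imprecise and serves as a complement.
- State that a non-significant stage comparison will not be read as absence of a shift.

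The cost is a few sentences. No new data or change in sample size is needed. The one drawback is the greater sensitivity to extra early tumours, which the rate per woman randomised helps to interpret.

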This could in particular be effective because the proposed populationbased screening study focuses on the group with the highest risk, for whom, at the same time, the effectiveness of the mammography is the most limited. The intended effect on a national level is as follows: Every year, there are about 900,000 women in the Netherlands between the age of 50 and 75 who are screened using mammography as part of the Dutch population-based mammography screening program. About 5% of these women have extremely dense breasts (>75% density), so 45,000 women. It is expected that adding an MRI to the mammography screening in this high-risk group will decrease the number of interval cancers from 4.4 per 1000 screened women to 1.44 per 1000 screened women (1;6) (calculations are explained further in section 7.7). On a national level, this means that the number of interval cancers per screening round in this group decreases from 199 to 65. The prognosis of patients with tumours discovered through screening is better than that of patients with interval cancers, with an estimated 5-year survival rate of 95% and 78% respectively (2). On the basis of these figures, we estimate that 23 deaths due to breast cancer could be prevented per screening round: 134 tumours (199 minus 65) detected now through screening instead of in the interval, and of which as a result thereof, 17% fewer breast cancer deaths in 5 years (95% minus 78%). From previous research in the screening population of 50-70 years, we know that the average age of women with >75% density is around 53 years. If we calculate with an average life expectancy of another 27 years, an additional 621 extra life years are gained per round with the proposed population-based screening study. In addition, this population-based screening study will have a favourable effect on the quality of life of breast cancer patients, considering a large part of the interval cancers (67%) will be diagnosed sooner through screening, which means an aggressive treatment will be required less frequently. 3. Natural course of the disease About 13,000 women in the Netherlands are diagnosed with breast cancer annually (Source: www.ikcnet.nl 2009). Three guarters of these women are 50 years or older (± 9,750). Important predictive factors for the prognosis of breast cancer are tumour diameter, axillary lymph node status and histologic tumour grade (1;15). In the Netherlands, women between the age of 50 and 75 are screened every two years using mammography as part of the Dutch population-based mammography screening program. The population-based screening program detects about 5,000 breast tumours each year (51% of all tumours among women older than 50) (1). However, not all tumours are detected through the population-based screening program: Among the participants, about 30% of the tumours are discovered in the interval between the screening rounds (the so-called interval cancers) (1). This large number of interval cancers is a problem since the staging, and with that the prognosis, is less favourable compared to the

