The MRI BI-RADS 3 results will be reassessed centrally *before* the results are reported back to the woman. With this double reading, by definition, the highest BI-RADS score is taken as the final result. The reason for reassessment of the BI-RADS 3 results is that this is typically the most difficult assessment category for the radiologists. This is because this is a very heterogeneous group of lesions, for which no clear classification category exists. All participating radiologists receive training to standardise the MRI procedures and assessment of MRI examinations.

5. Screening interval

The proposed experimental population-based screening study using mammography and MRI among women with very dense breasts will run parallel to the current Dutch breast cancer screening programme (2 year screening interval). This screening interval was chosen in the past based on a careful consideration of the costs and benefits. We continue with this, because there are no indications that women with very dense breasts in this age category develop other tumours (for example, faster-growing tumours) compared to women with fatty breasts. Besides, by adopting the current screening interval, the existing infrastructure can be used, which simplifies the research on the added value of MRI examinations.

6. Diagnosis

The MRI results lead to different strategies for further diagnostic work-up, as described in the Netherlands National Breast Cancer Dialogue (in Dutch: Nationaal Borstkanker Overleg Nederland, NABON) Mammary Carcinoma Directive (27):

- The MRI BI-RADS 0 result (=incomplete examination) is merely a temporarily result, and a completion of this examination will take place as soon as possible. A reason for a BI-RADS 0 result could be a technically incorrect execution of the MRI examination. The radiology department of the participating hospitals calls on the concerning woman to carry out a new MRI examination.
- When the MRI examination is negative (BI-RADS 1 or 2), further work-up is not required. Women with these scores will be invited again after 2 years for another mammography as part of the current

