screening trial results such as these, and to compare the cost-effectiveness of different screening measures (38;39). It is a validated model that has been applied numerous of times successfully in evaluating different screening strategies. It is also one of the most commonly used breast cancer models by the Cancer Intervention and Surveillance Modelling Network (CISNET) consortium sponsored by the National Cancer Institute (40). In MISCAN, the individual life courses are generated as a Markov process of stages and transitions. For this, the characteristics of the study population (demographic data, risk factors) are fed to the model. The results of the screening and the scenarios as applied in the proposed experimental population-based screening study are estimated for a cohort of 1 million women with very dense breasts. The effects on mortality and life vears gained with the different screening scenarios are estimated at a period of 10 years after the start of the screening. The most important parameters in the model are the average duration of the preclinical stages that can be detected with screening, sensitivity of the screening test and improvement in prognosis after detection through screening. Outcomes of the model are the number of screen-detected tumours and interval cancers (including stage distribution), age-specific breast cancer incidence, stratified by stage, and age-specific breast cancer mortality.

Analysis of cost-effectiveness

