The breast cancer simulation model will also be used to predict the costs and effects of different screening strategies for a situation in which the screening is carried out for 10 years. The costs of the diagnosis and treatment of breast cancer will be registered as part of the experimental population-based screening study. Costs and effects are calculated for a simulated cohort of 1 million women for a period of 10 years after the start of the screening. The costs are presented in euros. The effects are presented in terms of breast cancer mortality reduction and number of life years gained. Cost-effectiveness ratios (CER) are expressed in costs per life-year gained and incremental cost-effectiveness ratios (ICER) as extra costs per extra life-year gained. For the intervention group, the guality of life is assessed using the EuroQoI-5D questionnaire. To estimate the number of guality-adjusted life years of the control group, we use the EuroQol-5D health status data of the general population of Dutch women of the age between 50 and 75 (41). We implement weighting factors with a reduction of 10%, 25%, 40% for respectively non-metastatic tumours, tumours with metastases in the regional lymph nodes or tumours with distant metastases. For this reason, the ICER is expressed in extra costs per quality adjusted life-year gained.

Analysis of quality of life

The effect of MRI screening on the quality of life of the women will be assessed using questionnaires. The EuroQoI-5D questionnaire is a validated and a frequently-used questionnaire that is able to assess the quality of life with a few short questions, regarding physical as well as psychological consequences (41).

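### The cost-effectiveness model stops counting when its 10 years of screening stop, so cost per life-year gained is probably overstated against MRI; the baseline utility for QALYs also needs stating

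*Combined protocol and SAP*

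**What the plan says.** Part 7, section 9, *Analysis of cost-effectiveness*, uses the simulation model to predict costs and effects "for a situation in which the screening is carried out for 10 years". The next statement on the period is "Costs and effects are calculated for a simulated cohort of 1 million women for a period of 10 years after the start" of screening. Results are costs per life-year gained, then extra costs per QALY gained.

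*Estimation of mortality reduction*, in the same section, says that mortality and life-years "gained with the different screening scenarios are estimated at a period of 10 years after the start of the screening". It applies this to the scenarios as used in the trial, which Part 7, section 6 sets at 3 rounds in 6 years per participant.

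Part 3, section 5 says that the study "will run parallel to the current Dutch breast cancer screening programme (2 year screening interval").

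For QALYs, the plan names EuroQol-5D responses for the intervention group and Dutch general-population data for the control group. Utility falls by 10%, 25% or 40% according to tumour spread. No common baseline is named to which these reductions apply.

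The text available gives no longer horizon, no discount rate and no sensitivity analysis on the horizon.

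**The concern.** A screening round is paid for when it takes place, and its benefit arrives years later. If the accounting period ends with the screening period, early rounds have time to show their benefit and late rounds do not, yet all are charged in full. A round at year 8 has two years in which to avert a death. The ratio of cost to life-years then rises for a reason that has nothing to do with MRI.

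A second ambiguity makes this worse. The text does not say whether a woman whose death is averted before year 10 is credited with all her remaining life or only with the years up to year 10. These give very different answers.

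Cost-effectiveness is the second research question (Part 7, section 4), so a ratio biased against MRI could affect a decision on introducing it.

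The utility sources raise a separate, conditional question. If trial responders supply one strategy's utilities and population norms the other's, any difference between those two groups of women enters the incremental QALYs as though MRI had caused it.

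**Working it through.** **The plan's own benefit figure.** Part 2, section 2 takes 199 − 65 = 134 tumours moved from interval to screen detection and applies "17% fewer breast cancer deaths in 5 years (95% minus 78"%). 134 × 0.17 = 22.8, taken as 23 deaths. It continues: "If we calculate with an average life expectancy of another 27 years, an additional 621 extra life years are gained per round". 23 × 27 = 621, so the figure reproduces. Over the 45,000 women on whom it is based, this is 621 / 45,000 = 0.0138 life-years per woman per round.

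**Inputs for the horizon check.**
- Rounds at years 0, 2, 4, 6 and 8: from the 2-year interval and 10 years of screening.
- Would-be diagnosis uniform over the 2 years after a round: assumption.
- Would-be death uniform over the next 5 years: assumption, based on the plan's 5-year survival difference.
- Remaining life: either 27 years per averted death, or up to age 80. The latter is 53 + 27, since the plan says "the average age of women with >75% density is around 53 years".
- Incremental costs held fixed: assumption; the documents give no costs.

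Write D = round year + diagnosis delay (0 to 2) + survival time (0 to 5). Mean D is the round year + 3.5.

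| Round (year) | P(D > 10) | Averted deaths in window | Life-years to year 10 per averted death | Life-years to age 80 |
|---|---|---|---|---|
| 0 | 0% | 1.00 | 6.50 | 23.5 |
| 2 | 0% | 1.00 | 4.50 | 21.5 |
| 4 | 5% | 0.95 | 2.52 | 19.5 |
| 6 | 40% | 0.60 | 0.93 | 17.5 |
| 8 | 80% | 0.20 | 0.13 | 15.5 |
| Total | mean 25% | 3.75 | 14.58 | 97.5 |

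The last two rounds are 40% of the MRI rounds. They give 0.80 / 3.75 = 21% of the averted deaths in the window and 1.06 / 14.58 = 7% of the life-years in it.

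**Reading A: deaths averted by year 10 keep full remaining life.**
- 27 years each: 5 / 3.75 = 1.33.
- To age 80: each such death earns its years to year 10 plus 17 more, so 14.58 + 17 × 3.75 = 78.33, and 97.5 / 78.33 = 1.24.
- At 3% discounting (an assumed rate): 1.28 and 1.22.

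**Reading B: life-years are cut at year 10.**
- Death averted for good: 97.5 / 14.58 = 6.7 (to age 80) and 5 × 27 / 14.58 = 135 / 14.58 = 9.3. At 3%: 5.1 and 6.4.
- Death only postponed by 5 years: 25 life-years in all, 12.5 of them in the window, so 2.0. At 3%: 1.84.

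**Sensitivity to the time from diagnosis to death.** With up to 2 years, Reading A gives about 1.1 and Reading B about 1.5 to 6.6. With up to 10 years, Reading A gives 1.6 to 2.0 and Reading B about 3 to 16.

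**Costs after year 10.** The factor is (lifetime / 10-year life-years) × (10-year / lifetime net cost). It returns to 1 when the net cost after year 10 equals (factor − 1) × the 10-year net cost. That is 22% to 33% for Reading A (1.22 to 1.33) and 84% or more for Reading B (1.84 upwards). Net savings after year 10 would enlarge the factor.

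**Utility break-even.** This is the gap between the two sources that would equal the whole benefit.
- Full-life credit: 0.0138 / 2 years = about 0.007, held over a 2-year round.
- Life-years cut at year 10: 23 / 45,000 × 14.58 = 0.0075 life-years per woman over five rounds. Divided by 10 years, this is about 0.00075.

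These are break-even values, not estimates of a gap.

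**The case against.** Several points on the other side are sound.

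- **The mortality section does not repeat the problem in full.** A reader might infer that it too models 10 years of screening. It does not say so. It takes the trial's scenarios, 3 rounds in 6 years, and reads them at year 10. It shares the cut-off but leaves some follow-up after the last round. Equal screening and accounting periods rest on the cost-effectiveness paragraph alone.
- **There is no internal contradiction.** The sentence "Calculating the actual mortality reduction requires a very long follow-up period and an even larger study population than proposed here" might seem to promise a long model horizon. It only explains why the trial itself cannot observe mortality.
- **The size is weakly determined.** The factors depend on assumed timing of deaths, on how a death is credited and on fixed costs. The multi-fold figures need the harsher reading, which the text does not establish.
- **The utility point may be no more than wording.** The reductions by tumour spread are not limited to one arm, which fits a model with one baseline. Controls are deliberately not informed, so outside norms for them follow from the design. The questionnaire flowchart is not visible.
- **The document is a line-limited permit application** that refers to cited sources for the model.

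What remains is that the cost-effectiveness paragraph states a 10-year accounting period for 10 years of screening, and nothing in the text lengthens it.

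**Conclusion.** The horizon point holds. Cost per life-year gained is probably overstated, because every round's MRI costs are counted while part of the later rounds' benefit is not. Every timing, discounting and crediting case above gives a factor over 1 with costs fixed. "Probably" is as far as it goes, since net costs after year 10 of roughly a quarter to a third of the 10-year net cost would cancel the milder reading. The 1.2- to 1.3-fold and 2- to 9-fold figures are illustrations, not estimates.

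A reader might infer that cost per QALY is overstated too. That follows only if both strategies use one baseline utility. If the two sources are applied as written, a difference unrelated to MRI and of unknown sign enters the incremental QALYs and could offset or reverse the direction. The documents do not say which reading applies, so for QALYs this is a point to clarify, not a demonstrated bias.

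The matter should be corrected, but it concerns the economic analysis only.

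**What to change.** 1. Keep 10 years of screening in the model, but follow the simulated cohort for life for both costs and effects. State the discount rates.
2. Report the 10-year result as a sensitivity analysis, and say there how a death averted before year 10 is credited.
3. State one age-specific baseline utility for both strategies and apply the 10/25/40% reductions to both.
4. Use the trial EuroQol-5D data only for changes due to MRI: within-woman where a measurement before MRI exists, otherwise contrasts by MRI result within the intervention arm. The quality-of-life section already plans comparisons by MRI result.

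This costs changes to model settings and to the text, and needs no new data from control women. The drawback is that lifetime results lean more on model extrapolation, and lifetime treatment costs must be modelled as well. Whether a EuroQol-5D measurement before MRI exists cannot be told from the visible text; the within-arm contrast does not need one.
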